#### 9.2.3 Time to first response

The frequency and percentages of patients with a response (CR or PR) will be summarized by the first occurrence using the following time points;  $\leq 9$  weeks (Cycle 2),  $\leq 17$  weeks (Cycle 4),  $\leq 25$  weeks (Cycle 6),  $\leq 33$  weeks (Cycle 8), and  $\geq 33$  weeks.

#### 9.2.4 Population PK analyses

Sparse blood sampling for population PK analyses will be conducted in all patients treated with CO-1686. A specific population PK data analysis plan will be developed and will outline the detailed approach to data handling, model development and diagnostics, individual model parameter estimation,

#### 10 STATISTICAL/ANALYTICAL ISSUES

#### 10.1 Handling of Dropouts or Missing Data

All available data will be used to the greatest extent possible without any imputations for missing data.

# 10.2 Pooling of Centers in Multi-Center Studies

The data from all study centers will be pooled for analysis.

## 10.3 Multiple Comparison/Multiplicity

No adjustments for multiple comparisons will be made.

#### 11 SAFETY ANALYSIS

The safety analyses will be performed using the safety population.

#### 11.1 Adverse Events

Adverse events will be classified using the Medical Dictionary version 16.1 for Drug Regulatory Activities (MedDRA) classification system. The severity of the toxicities will be graded according to the NCI CTCAE whenever possible. Treatment-emergent adverse events (TEAEs) are defined as AEs with onset date on or after the date of first dose of study medication until the date of the last study medication dose plus 28 days. Adverse events will be considered treatment-emergent if all or part of the date of onset of the adverse event is missing and it cannot be determined if the adverse event meets the definition for treatment-emergent.

The number and percentage of patients who experienced TEAEs for each system organ class and preferred term will be presented. Multiple instances of the TEAE in each system organ class and multiple occurrences of the same preferred term are counted only once per patient. The number and percentage of patients with at least one TEAE will also be summarized.

14 of 17

Separate tables will be presented as follows:

- All TEAEs;
- TEAEs by CTCAE grade;
- Grade 3 or greater TEAEs;
- Treatment-related TEAEs;
- Serious TEAEs (SAE);
- Serious treatment-related TEAEs;
- TEAEs with an outcome of death;
- TEAEs leading to discontinuation of study medication; and
- TEAEs resulting in reduction, delay, or interruption of study medication.
- Time to the first adverse events that results in a reduction, delay, interruption or discontinuation of study drug.

The incidence of TEAEs will be summarized by relationship to study drug according to the following categories: "treatment-related," or "not treatment-related". The category of treatment-related is defined as a relationship of "Possible/Probable", "Definitely", or missing. If a patient experiences multiple occurrences of the same AE with different relationship categories, the patient will be counted once, as a relationship category of treatment related.

If a patient experiences multiple occurrences of the same AE with different toxicity grades, the patient will be counted once for the maximum (most severe) toxicity grade. AEs with a missing toxicity grade will be presented in the summary table with a toxicity grade of "Missing." For each toxicity grade, the number and percentage of patients with at least one TEAE of the given grade will be summarized.

The time to the first adverse event that results in a dose reduction, delay, interruption or discontinuation of study drug is defined as 1+ the number of days from the first dose of study drug to the start of the first adverse event. Patients without an event will be censored on the date of their most recent visit date.

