To date, there have been 11 deaths while on study or within 28 days after the last dose of rociletinib. Eight deaths were reported as due to progression of NSCLC, 1 death due to pulmonary embolism, 1 death due to pneumonia, and 1 death of unknown cause. At this stage, a causal relationship with rociletinib cannot be ruled out for the death of unknown cause; all other deaths were reported as unrelated to study drug.

Table 3-1: Treatment-related Serious Adverse Events Reported in Patients in Study CO-1686-008

SOC PT	< 900 BID FB (N = 38)	900 BID FB (N = 19)	500 BID HBr (N = 18)	625 BID HBr (N = 17)	750 BID HBr (N = 50)	1000 BID HBr (N = 6)	Overall (N = 148)
Number of Patients with at Least 1 Treatment-related Treatment-emergent SAE							
Overall	4 (10.5%)	1 (5.3%)	4 (22.2%)	3 (17.6%)	4 (8.0%)	1 (16.7%)	17 (11.5%)
Cardiac Disorders							
Pericarditis	1 (2.6%)	0	0	0	0	0	1 (0.7%)
Gastrointestinal Disorders							
Diarrhea	1 (2.6%)	1 (5.3%)	0	0	0	0	2 (1.4%)
Nausea	1 (2.6%)	0	1 (5.6%)	0	1 (2.0%)	0	3 (2.0%)
Pancreatitis	0	0	1 (5.6%)	0	0	0	1 (0.7%)
Vomiting	2 (5.3%)	0	1 (5.6%)	0	1 (2.0%)	0	4 (2.7%)
Infections and Infestations							
Gastroenteritis	0	0	0	0	1 (2.0%)	0	1 (0.7%)
Investigations							
ECG QT prolonged	0	0	0	1 (5.9%)	1 (2.0%)	0	2 (1.4%)
ECG T wave inversion	0	0	0	0	1 (2.0%)	0	1 (0.7%)
Transaminases increased	0	1 (5.3%)	0	0	0	0	1 (0.7%)
Metabolism and Nutrition Disorders							
Combined terms of hyperglycemia	1 (2.6%)	0	4 (22.2%)	1 (5.9%)	2 (4.0%)	1 (16.7%)	9 (6.1%)
Decreased appetite	0	1 (5.3%)	0	0	0	0	1 (0.7%)
Hypoglycemia	1 (2.6%)	0	0	0	0	0	1 (0.7%)
Hypokalemia	0	0	0	1 (5.9%)	0	0	1 (0.7%)
Respiratory, Thoracic, and Mediastinal Disorders							
Pneumonitis	0	0	0	1 (5.9%)	0	0	1 (0.7%)

Abbreviations: BID, twice daily; ECG, electrocardiogram; FB, CO-1686 free base; HBr, CO-1686 hydrobromide; N, number of patients; PT, preferred term; SAE, serious adverse event; SOC, system organ class.

Treatment-related Adverse Events (AEs)

Of the 148 patients treated with rociletinib as of the data cut-off date, 124 patients (84%) had at least 1 AE and 111 patients (75%) had an AE considered to be possibly, probably, or definitely related to rociletinib.

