10.6 Recording of Adverse Events and Serious Adverse Events

Any AE from the time the first dose of CO-1686 is administered through 28 days after the last dose, will be recorded on the AE eCRF. In addition, study procedure-related AEs that occur after signing of the ICF and before first dose of CO-1686 will also be captured on the AE eCRF. Any other AE that occurs prior to first dose of study drug should be recorded on the Medical History eCRF. In order to avoid vague, ambiguous, or colloquial expressions, the AE should be recorded in standard medical terminology rather than the patient's own words. Whenever possible, the investigator should combine signs and symptoms that constitute a single disease entity or syndrome. For example, fever, headache, and nasal discharge may be reported as coryza, if that is a reasonable diagnosis.

The existence of an AE may be concluded from a spontaneous report of the patient; from the physical examination; or from special tests such as the ECG, laboratory assessments, or other study-specified procedure (source of AE).

Each AE is to be evaluated for duration, severity, seriousness, and causal relationship to the investigational drug. The action taken and the outcome must also be recorded.

SAEs that occur during the study or within 28 days after receiving the last dose of CO-1686, whether or not related to CO-1686, must be immediately reported to the sponsor/designee SAE contact ([Section 10.8](#)). After the 28-day window, only SAEs that are considered treatment-related should be reported to the sponsor/designee within 24 hours of knowledge of the event. SAEs that are not considered treatment-related should be reported per local institutional or regulatory policy and practices, using the SAE form until alternative therapy has started.

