10.6.2 Causal Relationship of Adverse Events to Investigational Medicinal Products

Medical judgment should be used to determine the cause of the AE considering all relevant factors such as, but not limited to, the underlying study indication, coexisting disease,

concomitant medication, relevant history, pattern of the AE, temporal relationship to the study medication, dechallenge or rechallenge.

Not Related

- An AE that is clearly due to extraneous causes (eg, concurrent disease, concomitant medications, disease under study, etc.)
- It does not follow a reasonable temporal sequence from administration of study drug
- It does not follow a known pattern of response to study drug
- It does not reappear or worsen when study drug is restarted
- An alternative explanation is likely but not clearly identifiable

Related

- An AE that is difficult to assign to alternative causes
- It follows a strong or reasonable temporal sequence from administration of study drug
- It could not be reasonably explained by the patient's clinical state, concurrent disease, or other concomitant therapy administered to the patient
- It follows a known response pattern to study drug
- It is confirmed with a positive rechallenge or supporting laboratory data

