11.2.5.2 Adverse Events

AE coding will be performed using MedDRA. The severity of the toxicities will be graded according to the NCI CTCAE v4.03 whenever possible. Treatment-emergent AEs are defined as

AEs with an onset date on or after the date of first dose of CO-1686 until the date of the last CO-1686 dose plus 28 days. AEs will be considered treatment-emergent if all or part of the date of onset of the AE is missing and it cannot be determined if the AE meets the definition for treatment-emergent.

The number and percentage of patients who experienced treatment-emergent AEs for each SOC and PT will be presented. Multiple instances of the treatment-emergent AEs in each SOC and multiple occurrences of the same PT are counted only once per patient. The number and percentage of patients with at least 1 treatment-emergent AE will also be summarized.

Separate tables will present the following:

- All treatment-emergent AEs
- Treatment-emergent AEs by CTCAE grade
- Grade 3 or greater treatment-emergent AEs
- Treatment-related, treatment-emergent AEs
- Serious treatment-emergent AEs
- Treatment-emergent AEs with an outcome of death
- Treatment-emergent AEs leading to discontinuation of PO CO-1686
- Treatment-emergent AEs resulting in interruption or reduction or delay of CO-1686

The incidence of treatment-emergent AEs will be summarized by relationship to PO CO-1686 using “treatment-related” and “not treatment-related” categories. If a patient experiences multiple occurrences of the same AE with different relationship categories, the patient will be counted once as a relationship category of treatment-related.

If a patient experiences multiple occurrences of the same AE with different intensity toxicity grades, the patient will be counted once for the maximum (most severe) toxicity grade. AEs with a missing intensity will be presented in the summary table with a toxicity grade of “Missing.” For each toxicity grade, the number and percentage of patients with at least 1 treatment-emergent AE of the given grade will be summarized.

Non-treatment-emergent AEs (pretreatment and post-treatment) will be presented in the data listings.

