# 2.2 Sample Size used

Approximately 125 patients are planned to be enrolled under the protocol and subsequent Amendments for the MAA and NDA.

For the initial MAA and NDA submissions all patients enrolled in this trial by the 31st of December 2014 with a data cutoff date of April 2015 will be used for both efficacy and safety conclusions. The efficacy and safety profile for CO-1686 will be established by the combined patients treated in this study and Phase 1 study, CO-1686-008.

Confidential 7 of 17

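### The SAP's definition of a treatment-related AE omits 'Related', the only positive causality category in the supplied protocol

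*SAP*

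**What the plan says.** Protocol 10.6 requires a causality judgement for every adverse event: "Each AE is to be evaluated for duration, severity, seriousness, and causal relationship to the investigational drug". Protocol 10.6.2 supplies the scale. It has two categories, each with its own criteria. 'Not Related' opens with "An AE that is clearly due to extraneous causes" and 'Related' opens with "An AE that is difficult to assign to alternative causes". There are no intermediate levels.

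Protocol 11.2.5.2 carries the same two-way split into the analysis: "The incidence of treatment-emergent AEs will be summarized by relationship to PO CO-1686 using “treatment-related” and “not treatment-related” categories". It gives no rule for missing causality.

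SAP 11.1 keeps the two summary categories but builds the first from a different set of values: "The category of treatment-related is defined as a relationship of 'Possible/Probable', 'Definitely', or missing". It does not say which values make up the second. It lists treatment-related TEAEs and serious treatment-related TEAEs as separate tables and adds a summary of incidence by relationship. SAP section 12, which lists departures from the protocol's analyses, does not mention the causality definition.

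**The concern.** The SAP's list and the protocol's scale share no recorded value. An event that an investigator scores as 'Related' under protocol 10.6.2 matches nothing in the SAP definition, while an event with no causality entry does match. A rule meant to identify drug-related toxicity would then select on absence of data.

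The tables at stake support a regulatory submission. SAP 2.2 says: "The efficacy and safety profile for CO-1686 will be established by the combined patients treated in this study and Phase 1 study, CO-1686-008". The protocol's background section describes CO-1686-008 in graded terms, reporting patients who "had an AE considered to be possibly, probably, or definitely related to rociletinib". If one study is recorded on two levels and the other on a graded scale, the combined tables need a stated mapping, and none is given.

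**Working it through.** The plan states no figure on this point. The check is a comparison of the texts, followed by a bound on the size.

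**Step 1. Apply the SAP rule to each value that the protocol's scale allows.**

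| Value under protocol 10.6.2 | In the SAP 11.1 list? | Category if the rule is followed literally |
|---|---|---|
| Related | No | Not treatment-related (by default) |
| Not Related | No | Not treatment-related (by default) |
| Missing | Yes | Treatment-related |

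'By default' matters: SAP 11.1 does not define the not-treatment-related category, so 'Related' is unmapped rather than expressly excluded. It falls there only because the summary has two categories.

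**Step 2. Find which outputs use the definition.** In SAP 11.1 these are the treatment-related TEAE table, the serious treatment-related TEAE table and the by-relationship summary. The tables of all TEAEs, TEAEs by grade, Grade 3 or greater, serious, fatal, leading to discontinuation and leading to dose modification do not use it. Nor does the time to first AE leading to dose modification or discontinuation. ORR is not touched.

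**Step 3. Look for a passage that resolves the mismatch.** Protocol 11.2.5.2 names the two summary categories without a mapping. SAP section 12 lists no change. Graded causality wording appears in the protocol only in section 3.4.1.1, about CO-1686-008. The SAP wording may have been carried over from that study, but this is an inference.

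**Step 4. Bound the size.** Assumptions: the CO-1686-008 rates in protocol Tables 3-1 and 3-2 apply, there are 125 patients (SAP 2.2), all causality is recorded as 'Related' or 'Not Related', and no affected patient also has an event with missing causality.

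Formula: patients removed = 125 × rate.

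| Rates used | Related AE | Related SAE |
|---|---|---|
| All doses (N = 148) | 125 × 111/148 = 93.8, about 94 | 125 × 17/148 = 14.4, about 14 |
| 625 mg BID HBr (N = 17) | 125 × 15/17 = 110.3, about 110 | 125 × 3/17 = 22.1, about 22 |
| 750 mg BID HBr (N = 50) | 125 × 28/50 = 70 | 125 × 4/50 = 10 |

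The all-dose row includes 38 + 19 = 57 patients on the free-base formulation. The 625 mg row matches the Cohort A dose but rests on 17 patients. The 750 mg row has the lowest rates among the HBr doses and shows the spread. Each figure is the most that a literal reading could remove at those rates. A patient who also had an event with missing causality would stay in the table.

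**The case against.** The strongest reply is that the two documents are not of the same date. SAP section 1 says that it implements the original protocol and Amendments 1 to 3; the protocol supplied is Amendment 5. The SAP plainly follows an older text: it has a 28-day biopsy window where the protocol has 60 days, only T790M-positive patients, and no Cohort B. The causality wording in force at Amendment 3 is not in the documents, and nor is the eCRF code list, which fixes what sites enter. A graded scale may have been in use when the SAP was written. This limit stands. It does not remove the need for a correction. If the eCRF has two levels, the SAP omits its key value. If it is graded, it disagrees with the current protocol 10.6.2. If the scale changed during the study, a mapping is needed to join the two parts.

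A second reply is that the intent of SAP 11.1 is inclusive. Missing causality counts as related, and so does any conflict between occurrences of the same event. A programmer might well map 'Related' correctly, and a table holding only events with missing causality would be noticed. This also stands, and it limits the claim to the rule as written.

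Three stronger readings are tempting, and the documents do not support them:

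- A reader might infer that sites recorded 'Related' and that the submission tables therefore understated toxicity. The recorded codes are not available, and the mapping a programmer used cannot be known.
- A reader might infer that the secondary safety endpoint is compromised. That endpoint is treatment-emergent AEs regardless of causality, and most of its tables do not depend on the definition.
- A reader might count the treatment of missing causality as part of the error. It is a conservative choice and should be kept.

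**Conclusion.** The concern holds as a defect in a stated rule. Applied literally to the causality scale in the supplied protocol, SAP 11.1 puts only events with missing causality in the treatment-related category. That affects two named tables and one summary, and nothing else. This goes beyond missing detail, because the rule that is given yields the wrong classification for that scale.

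The patient counts under working are ceilings, not predictions. They rest on borrowed rates and complete misclassification. They also use the planned 125, whereas the NDA analysis covers patients enrolled by 31 December 2014, a number that the SAP does not give. The correction should be made before the tables are relied on. Confidence is medium, because the Amendment 3 wording and the eCRF codes cannot be seen.

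**What to change.** Replace the SAP 11.1 sentence with: *treatment-related = Related, Possible/Probable, Definitely, or missing; not treatment-related = Not Related.* This covers both a two-level and a graded scale and keeps the conservative handling of missing causality.

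Then check the list against the causality codes actually held in the database, so that every recorded value falls in exactly one category. State that the same mapping applies when this study is combined with CO-1686-008. If the recorded scale proves to be graded, reconcile it with protocol 10.6.2.

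The cost is a sentence or two in the SAP and one format mapping in the programs. No new data are needed.

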9.4 Two Monthly Follow-up

The following procedures will be performed every 8 weeks \pm 7 days (unless otherwise specified) following the End-of-Treatment Visit:

- Survival status - This may be performed during routine clinic visits or by telephone contact.
- Subsequent therapies for NSCLC will be documented during routine clinic visits or by telephone contact.

- If a patient discontinues treatment before progression, then scans should continue until progression according to the protocol schedule of every 8 ± 1 weeks. Exceptions to this requirement may be acceptable based on local institutional or regulatory requests and must be approved in advance by the sponsor.

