#### 2 OVERALL STUDY DESIGN AND OBJECTIVES

## 2.1 Trial Design and Study Procedures

This is a Phase 2, single arm, open-label, multicenter study evaluating the safety and efficacy of CO-1686 administered orally twice daily to patients with previously treated mutant EGFR NSCLC whose tumor harbors the T790M resistance mutation. The central laboratory will confirm that the patient's tumor harbors the T790M mutation using biopsy material obtained from either primary or metastatic tumor tissue within 28 days of dosing with study drug and after progression on EGFR directed therapy.

CO-1686 will be administered to patients twice daily. Patients will take CO-1686 with a meal or within 30 minutes after a meal. Treatment with CO-1686 is continuous. Each 28 day period of treatment will represent one cycle, with dosing initiated on C1 D1. No dose escalation beyond the starting dose is allowed.

Patients will undergo serial assessments for anti-tumor efficacy, drug safety, and patient reported outcomes (see Section 9 of the Protocol). Sparse blood sampling for population PK analyses will be conducted in all patients treated with CO-1686. Serial blood sampling for longitudinal quantitative assessment of ctDNA will be conducted. Central laboratories will be used for hematology and chemistry, as well as for ECG interpretation.

Tumor scans will be acquired by the investigative site and evaluated locally for patient treatment decisions; however, copies of tumor scans will be sent to a independent radiological review (IRR) vendor. Protocol-specified treatment will continue until there is RECIST or clinical tumor progression or unacceptable toxicity as assessed by the investigator. Following disease progression on CO-1686 and discontinuation of protocol-specified treatment, patients who provide additional consent will undergo tumor biopsy before subsequent-line therapy is initiated. After discontinuation of protocol-specified treatment, subsequent anticancer therapy will be recorded.

All patients should return to the clinic for end-of-study assessments 28 (±7) days after the last dose of oral CO-1686 has been administered. The trial will be completed when all cnrolled patients have discontinued treatment in this protocol and completed the end-of-study follow-up visit.

All patients will be followed at approximately two monthly intervals to monitor survival status and subsequent NCSLC cancer therapy until death or sponsor decision, whichever comes first.

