# 11.2 Clinical Laboratory Evaluations

In this study, blood will be sent for analysis to a central laboratory for all cycles Day 1 visits, in addition to collecting the local lab results. The focus of the report will be based on these central laboratory results for all summary tables. Listings will be presented with both the central and local lab results. In addition, since glucose is a laboratory variable of interest the analyses around glucose will include both the central laboratory results and the local laboratory results.

Clinical laboratory evaluations include the continuous variables for hematology, serum chemistry, and urinalysis. Laboratory values will be presented in Standard International units. The baseline laboratory value will be defined as the last value prior to or on the day of the first dose of oral CO-1686. The on-treatment period will be defined as the day after the first dose of

oral CO-1686 to 28 days after the last dose of CO-1686. Laboratory values collected during the on-treatment period will be included in the summary tables. The laboratory values collected after the on-treatment period will only be presented in the data listings.

The summary of laboratory data will include descriptive statistics (N, mean, standard deviation, minimum, median, and maximum) of the maximum, minimum, and last value during the treatment period by dose group and study phase. Summaries using descriptive statistics of the change from baseline to the maximum, minimum, and last value during the on-treatment period will also be given by dose group and study phase. Separate listings will be produced for clinically significant laboratory abnormalities (i.e., those that meet Grade 3 or 4 criteria according to CTCAE).

The time to first Glucose value > 13.875 mmol/L will also be summarized. The time to first occurrence of a glucose value > 13.875 mmol/L will be calculated as 1+ the number of days from study drug start date to the first date of the glucose value > 13.875 mmol/L. Patients who do not have an observed glucose value > 13.875 mmol/L will be censored on the date of their last visit or data cutoff date for ongoing subjects.

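### Two time-to-event safety analyses censor at an undefined last visit or at the data cutoff, so on-treatment risk can come out too low by an amount that depends on what counts as a visit

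*SAP*

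**What the plan says.** SAP 11.1 analyses the time to the first adverse event that changes, pauses or ends dosing. The time is "defined as 1+ the number of days from the first dose of study drug to the start of the first adverse event", and the censoring rule is "Patients without an event will be censored on the date of their most recent visit date".

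SAP 11.2 analyses the time to the first glucose above 13.875 mmol/L. Patients without such a value "will be censored on the date of their last visit or data cutoff date for ongoing subjects".

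Neither section defines a visit, and 11.2 does not define ongoing. In SAP 7 (exposure) ongoing appears to mean still on treatment. SAP 3 names Kaplan-Meier for duration of response, PFS and OS only, so no estimator is named for these two times.

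The same SAP bounds its other safety summaries by exposure. Treatment-emergent events run "until the date of the last study medication dose plus 28 days". The on-treatment laboratory window runs from the day after the first dose of "oral CO-1686 to 28 days after the last dose of CO-1686".

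After stopping, patients return for "end-of-study assessments 28 (±7) days after the last dose" (SAP 2.1). Protocol 9.3 collects adverse events and fasting glucose at that visit. Contact then continues: "All patients will be followed at approximately two monthly intervals to monitor survival status" (SAP 2.1). Of the survival check, Protocol 9.4 says: "This may be performed during routine clinic visits or by telephone contact". It schedules neither adverse-event nor glucose assessment at these contacts.

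**The concern.** A patient who has permanently stopped CO-1686 has no dose left to modify, so the SAP 11.1 event can no longer occur. If that patient is censored at a later visit, the time in between adds to the risk set without any possibility of an event. For glucose, no sample is scheduled after the End-of-Treatment visit, so later time is unobserved. The glucose rule has a second gap: patients still on drug are carried to the data cutoff rather than to their last sample.

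Only patients who stop for reasons other than an adverse event matter in SAP 11.1, because those who stop for an adverse event are counted as events.

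These analyses describe how soon patients need a dose change and how soon marked hyperglycemia appears, in a SAP written for the NDA and MAA. Added event-free time can only lower an on-treatment estimate or leave it unchanged.

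**Working it through.** The documents state no event rate, power or sample size for these two analyses, so there is no plan figure to reproduce. Direction follows from the definitions. Size needs assumptions.

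**From the documents.** Enrolment closes 31 December 2014 and the cutoff is 29 April 2015, so follow-up is at least 119 days. Cycles last 28 days. The End-of-Treatment (EOT) visit is at about last dose + 28 days. Later contacts come about every 8 weeks.

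**Assumed, first set.** Uniform entry from 9 May to 31 December 2014 (follow-up 119 to 355 days). Exponential stopping for other reasons, median 120, 180 or 270 days. On-treatment risk of 30% or 50% by day 180, with hazard constant or front-loaded (Weibull, shape 0.4). No event after stopping. 300,000 simulated patients per scenario.

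Kaplan-Meier risk at day 180 (%) when the on-treatment risk is 50%:

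| Median stop, hazard | Censor at end of exposure | AE rule, EOT visit | AE rule, two-monthly contacts | Glucose rule, EOT or cutoff | Glucose rule, contacts or cutoff |
|---|---|---|---|---|---|
| 120 d, constant | 50.1 | 45.5 | 33.7 | 44.8 | 33.5 |
| 120 d, front-loaded | 49.9 | 46.6 | 40.9 | 46.2 | 40.8 |
| 180 d, constant | 50.0 | 47.2 | 38.4 | 46.4 | 38.1 |
| 180 d, front-loaded | 50.0 | 47.9 | 43.7 | 47.5 | 43.6 |
| 270 d, constant | 50.1 | 48.6 | 42.2 | 47.7 | 41.7 |
| 270 d, front-loaded | 50.0 | 48.7 | 45.7 | 48.3 | 45.4 |

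- *EOT reading.* The largest AE loss is 50.1 − 45.5 = 4.6 points. The smallest, with 30% risk (270 d, front-loaded), is 30.1 − 29.2 = 0.9. For glucose the range is 1.2 to 5.3.
- *Two-monthly reading.* The largest AE loss is 50.1 − 33.7 = 16.4 points and the smallest 30.1 − 27.2 = 2.9. For glucose the range is 3.0 to 16.6.
- *Ongoing patients, glucose.* Carrying on-drug patients to the cutoff instead of the last Day 1 visit costs a further 0.4 to 0.9 points in these rows (for example 48.6 − 47.7 = 0.9). The unmeasured gap is roughly one 28-day cycle at most.
- *Day 21.* The largest loss is 25.3 − 24.5 = 0.8 points.

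**Assumed, second set.** Follow-up 4 to 10 months, median stopping 4, 6 or 9 months, Weibull shape 1 or 0.6, median survival after stopping 23 months. With on-drug risk of 60% at six months, the AE rule gives 42, 48 and 51% (constant) or 47, 51 and 54% (front-loaded) if contacts count, a loss of 6 to 18 points. It gives about 55 to 59% if the EOT visit is last. With on-drug risk of 40%, counting contacts gives about 27 to 36%, a loss of 4 to 13 points.

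**Comparison with cumulative incidence.** With constant event hazard λ and stopping hazard μ, the probability of an event by time T before stopping is λ/(λ+μ) × (1 − exp(−(λ+μ)T)).

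- 50% risk, median stop 180 d: λ = μ = ln 2/180, giving 0.5 × (1 − 0.25) = 37.5%. The two-monthly reading gives 38.4%.
- 30% risk, median stop 120 d: λ = 0.001982, μ = 0.005776, giving 0.2554 × (1 − exp(−1.396)) = 19.2%. The two-monthly reading gives 19.7%; censoring at end of exposure gives 29.9%.
- Second set, 60% risk: cumulative incidence is 40, 46 and 50% (constant) and 46, 50 and 53% (front-loaded), about 1 to 2 points below the two-monthly figures.

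**The case against.** A reader might infer that the SAP's event rates are simply too low and that the drug will look better tolerated than it is. The documents do not support that, for four reasons.

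First, too low presupposes a target that the SAP does not state. Against the share of patients who actually have the event before stopping for another reason, the two-monthly reading is close and slightly high. Censoring at last dose then reports something different: the risk if nobody stopped for other reasons. This stands, and it is why both quantities should be reported.

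Second, the large figures need two-monthly contacts to count as visits. SAP 2.1 treats the 28-day attendance as the end-of-study visit, and later contacts may be by telephone. On that reading adverse-event censoring falls near the end of the SAP's own treatment-emergent window, and glucose censoring for stopped patients falls on the last scheduled sample. This also stands, but the SAP does not exclude the wider reading. Table 9-1 lists follow-up as a scheduled time point, and patients who stop before progression keep having scans. Appendix C ends participation at the EOT visit, but it belongs to Amendment 5, after this cutoff.

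Third, Protocol 7.4 says hyperglycemia generally arises in the first three weeks, where the effect is under 1 point. That limits the glucose concern, though not the dose-modification analysis.

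Fourth, both analyses are descriptive and single-arm, and the crude tables of dose-modifying events are untouched. Correct; this bounds the consequence.

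**Conclusion.** The defect is real but modest. Both rules can count stopped patients as at risk when no event can occur or be observed, and the glucose rule also adds unmeasured time for patients on drug. On-treatment Kaplan-Meier estimates can therefore be too low at six months: by about 1 to 5 points if the last visit is the EOT visit, and by about 3 to 18 points if two-monthly contacts count (3 to 17 in the first set of inputs, 4 to 18 in the second). In that second case the estimate approximates the competing-risk cumulative incidence. As written, the rules fix on neither target: with 60% on-drug risk the answer can fall anywhere from about 42% to 59%, depending partly on an undefined word.

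All sizes rest on assumed event and stopping rates, on no event after stopping, and on Kaplan-Meier being the estimator. The 23-month survival input is borrowed from the 1.9 years in Protocol 3.2, which describes survival after progression on a prior TKI and is only a stand-in. Early risk and crude treatment-emergent percentages are essentially unaffected.

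**What to change.** - **SAP 11.1.** For the on-treatment estimate, censor event-free patients who have stopped at last dose, or at the latest at last dose + 28 days to match the treatment-emergent window. Keep on-drug patients censored at their most recent visit with adverse-event assessment on or before the cutoff. Moving them to the cutoff itself would add unassessed time.
- **SAP 11.2.** Censor at the last glucose measurement on or before the earlier of last dose + 28 days and the data cutoff, for stopped and ongoing patients alike.
- **Both.** Define visit and ongoing, name the estimator, and state that the target is on-treatment risk. Report beside it the cumulative incidence with stopping for other reasons as a competing event.

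Cost: a few sentences, one derived censoring date per analysis and one added summary. No new data are needed. The on-treatment estimates will probably be slightly less favourable.
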